8.0 Data and Specimen Banking For Future Undetermined Research

8.1 Data and/or specimens being stored – N/A

8.2 Location of storage – N/A

8.3 Duration of storage – N/A

8.4 Access to data and/or specimens – N/A

8.5 Procedures to release data or specimens – N/A

8.6 Process for returning results– N/A**9.0 Statistical Plan****9.1 Sample size determination**

Sample size was determined based on a review of prior studies that used the VAS as the main outcome tool. A total sample size of 221 was determined based on the number needed to detect a difference of 5 mm assuming a standard deviation of 10 mm in the VAS and when also considering a 15 % drop out rate. 221 total patients initially enrolled in the study would account for 64 patients per treatment arm (Corticosteroid only v corticosteroid/lidocaine v corticosteroid/saline). Public Health Sciences will be ensuring accuracy of statistical analyses. Stratification based on perioperative variables of interest will not be necessary in our study. Instead, we will be analyzing these variables via subgroup multivariate analyses at the conclusion of the study.

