9.2 Statistical methods

The daily average pain score (VAS) will be compared between groups using either t-test or Wilcoxon test for each of the 6 days after the operation. Chi-square tests will be used to compare treatment groups for categorical variables (satisfaction, presence of clicking/locking, adverse events). Level of significance will be set at $p < 0.05$.

Secondary statistical analysis will include multivariate analyses to determine which variables such as anatomic location and comorbidities will impact the VAS score or modify the efficacy of injection. These can be accomplished by adding these variables and their interaction with treatment groups in the regression model. As these are secondary analysis, any interesting findings will be subject to validation in future studies.

Any deviations from the previously described statistical plan will be described and justified in a protocol amendment.

All analyses comparing the treatment groups will be conducted on an intention-to-treat basis. Two-tailed tests will be used at all times.

There will be an interim analysis when 50 % of patients (n=111) are enrolled and have completed final visit testing.

10.0 Confidentiality, Privacy and Data Management**10.1 Confidentiality****10.1.1 Identifiers associated with data and/or specimens**

See the Research Data Plan Review Form

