12.0 Risks

- Loss of confidentiality will be minimized as the research team will only have access to the research data and all information will be kept on a password-protected computer or in a locked filing cabinet.
- Subjects will be assigned to a treatment program by chance. The treatment received may prove to be less effective or to have more side effects than the other research treatment(s) or other available treatments.

- Allergic reaction to lidocaine or the preservative used in lidocaine.
- Nerve damage for a period of time after the injection.

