16.0 Number of Subjects

Approximately 222 people (74 per treatment arm) will be enrolled in this research study at the Hershey Medical Center.

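### Section 9.2 tests adverse events by chi-square with no rule for small counts; if events are rare, some tables would get the wrong verdict at 0.05, although overall type I error is not inflated.

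*Combined protocol and SAP*

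**What the plan says.** Section 1.3 lists the incidence of adverse effects as a secondary endpoint, and section 1.1 makes review of adverse events in the three groups an objective. Section 9.2 names the test: "Chi-square tests will be used to compare treatment groups for categorical variables (satisfaction, presence of clicking/locking, adverse events"). The significance level is 0.05, and "Two-tailed tests will be used at all times". On the analysis set the same section says "All analyses comparing the treatment groups will be conducted on an intention-to-treat basis", with no exception for safety data.

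Section 9.2 names no exact test, continuity correction or small-count rule. It does not say whether adverse events are compared across all three arms at once (2 degrees of freedom) or in pairs.

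Section 12.0 lists the physical risks without frequencies: "Allergic reaction to lidocaine or the preservative used in lidocaine", and temporary nerve damage. On numbers, section 16.0 says "Approximately 222 people (74 per treatment arm) will be enrolled", and section 9.1 says "221 total patients initially enrolled in the study would account for 64 patients per treatment arm".

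**The concern.** The chi-square p-value is a large-sample approximation, and the usual working rule asks for expected counts of at least 5. Each patient has one injection, and sections 11.8 and 21.7 describe the drugs as approved and safe, so few patients per arm may have an event. A handful of events would then decide the safety comparison between the lidocaine and non-lidocaine mixtures. In some tables the planned test would report a significant difference where an exact test would not.

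A smaller point concerns grouping. Under intention-to-treat without exception, an event in a patient who was given the wrong mixture counts against the assigned mixture. A reaction to lidocaine in a patient assigned to corticosteroid/saline would be booked to that arm.

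**Working it through.** **Inputs.** Alpha is 0.05 two-sided (9.2). Patients per arm are 74 enrolled (16.0), 64 after dropout (9.1) and 37 at the interim (111/3, from 9.2). The adverse event rate is not given, so it is varied below.

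**The plan's own figure.** The plan states no figure for the adverse event comparison. Its sample size does reproduce. For a 5 mm difference, SD 10 mm and 80% power (power is not stated; this is assumed), 2 × (1.96 + 0.84)² × (10/5)² = 62.7, so 63 per arm, or 64 with the t distribution. Then 3 × 64 × 1.15 = 220.8, so 221. The 222 in section 16.0 is 3 × 74.

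**When counts are small.** With equal arms and T patients with an event, the expected count per arm is T/3, which is below 5 when T < 15. That is 15/222 = 6.8% at 74 per arm, 15/192 = 7.8% at 64, and 15/111 = 13.5% at the interim.

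**Three-arm test, 3/0/0 at 74 per arm.** Expected counts are 1 event and 73 non-events per arm.
- Chi-square = (4 + 1 + 1)/1 + (4 + 1 + 1)/73 = 6.08 on 2 df, so p = exp(−3.04) = 0.048.
- Exact p = 3 × C(74,3)/C(222,3) = 3 × 64,824/1,798,940 = 0.108.
- At 64 per arm the pair is 0.0475 and 0.1076; at 37 it is 0.0458 and 0.1051.

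**Other three-arm tables at 74 per arm** (Pearson chi-square; exact Freeman-Halton):

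| Events | Chi-square p | Exact p | Verdict at 0.05 |
|---|---|---|---|
| 4/0/0 | 0.017 | 0.035 | same |
| 5/1/0 | 0.027 | 0.0496 | same |
| 6/1/1 | 0.039 | 0.053 | significant by chi-square only |
| 6/5/0 | 0.052 | 0.032 | significant by exact test only |

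**Pairwise tests at 74 per arm.** For 4 v 0 the expected counts are 2 events and 72 non-events per arm. Chi-square = (4 + 4)/2 + (4 + 4)/72 = 4.11, p = 0.043. Fisher's p = 2 × C(74,4)/C(148,4) = 0.120.

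| Events | Uncorrected chi-square p | Continuity-corrected p | Fisher p |
|---|---|---|---|
| 3 v 0 | 0.080 | 0.243 | 0.245 |
| 4 v 0 | 0.043 | 0.128 | 0.120 |
| 5 v 0 | 0.023 | 0.069 | 0.058 |

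**Error rate of the three-arm chi-square at 74 per arm, no true difference.**
- Given the total number of events (all tables enumerated): 10.8% at exactly three events, and between 0% and 6.1% at every other total up to 15. At 4, 5, 6, 7 and 9 events it equals that of the exact test; at 11 events it is lower (3.2% v 4.6%).
- Averaged over the totals that would occur (three independent binomial counts enumerated): 0.1% at an incidence of 0.2%, 2.7% at 1%, 3.9% at 2%, 4.6% at 5% and 4.8% at 10%.

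**Interval.** For zero events in 74 the exact two-sided 95% upper limit is 1 − 0.025^(1/74) = 4.9%.

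**The case against.** The strongest reply is that the planned test controls its error rate. Averaged over event counts, the three-arm chi-square stays below 5% at every incidence listed above. The 3/0/0 table is its worst case, and many sparse tables lead to the same verdict. This stands, and it rules out the reading that the plan produces too many false safety alarms overall.

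A reader might also take rarity as given. The documents do not support that. Section 12.0 gives no frequencies, section 21.1 defines an adverse event as any untoward occurrence whether or not drug-related, and section 11.3 collects events for six weeks. Patients with any event could exceed 15 of 222, and the small-count problem would then not arise for that total.

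The 3/0/0 result needs a single three-arm test, which section 9.2 does not specify; in pairs, 3 v 0 is not significant. A continuity correction would bring 4 v 0 and 5 v 0 to Fisher's verdict. Both points are correct. But section 9.2 does not specify a correction either, and either reading of it contains tables where the verdict changes.

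Section 9.1 has Public Health Sciences ensuring the accuracy of the analyses, and section 9.2 allows deviations by amendment. A later switch is therefore possible, but neither provision supplies the missing rule, and a test chosen after the table is seen is harder to defend.

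On grouping, the physician who prepares the mixture also gives the single injection, so mix-ups should be uncommon, and the documents give no rate.

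**Conclusion.** The concern holds in a limited form. Section 9.2 names a large-sample test for adverse events, has no rule for small expected counts, and leaves the comparison undefined. If fewer than 15 patients have an event (6.8% of 222 or 7.8% of 192), the p-value can fall on the wrong side of 0.05 in particular tables: 0.048 v 0.108 for 3/0/0 and 0.039 v 0.053 for 6/1/1 in a three-arm test, and 0.043 v 0.120 for 4 v 0 and 0.023 v 0.058 for 5 v 0 in uncorrected pairwise tests. The error can also run the other way, as 6/5/0 shows.

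This rests on the assumption that events are rare and, for each example, on the stated form of the test. It is a minor defect in a secondary safety endpoint. A reader might infer that the plan would treat a non-significant result as proof of safety. Nothing in it says so, and an exact test would not prevent that inference. The 4.9% upper limit after zero events in 74 is a reason to report intervals, not evidence of an error in the plan.

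**What to change.** In section 9.2:
- State whether adverse events are compared in one three-arm test or in pairs, and if in pairs, which.
- Use Fisher's exact test (Freeman-Halton for three arms) when any expected count is below 5.
- Count patients with at least one event, and for this analysis group them by the injection actually received, as a stated exception to intention-to-treat.
- Report exact 95% intervals alongside the p-value.

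The cost is a short edit and a slightly more conservative test. It is best made before any comparison of the arms, including the interim analysis, because section 9.2 requires deviations from the plan to be described and justified in an amendment.

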1.2 Primary Study Endpoints

- Compare pain and efficacy associated with the three treatment groups.
 - VAS and mean daily pain values

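### Section 9.2 tests the three-arm primary VAS outcome pair by pair at an unadjusted 0.05, with no overall test and no named or ranked contrasts; if any significant pair can carry a claim, familywise error is about 9% to 12% at one time point

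*Combined protocol and SAP*

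**What the plan says.** Section 1.2 gives the primary endpoint as "Compare pain and efficacy associated with the three treatment groups", measured by VAS and mean daily pain. The first objective in Section 1.1 is to compare VAS pain after CSL with pain after CS and after CSS. Section 2.2 hypothesises that lidocaine adds pain, describes saline as the equal-volume comparator, and separately asks whether injected volume affects pain immediately after injection.

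In Section 9.2 the daily average VAS is to be "compared between groups using either t-test or Wilcoxon test for each of the 6 days" following the procedure. The same section adds "Two-tailed tests will be used at all times" and "Level of significance will be set at $p < 0.05". It gives no overall three-arm test for VAS, no list or ranking of pairs and no adjustment. Its only regression model is a secondary analysis of covariates and their interactions with treatment.

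Sections 7.2.1 to 7.3 schedule VAS before injection, at 1 and 10 minutes after it, and by telephone at 6 weeks.

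Section 9.1 bases the sample size on "the number needed to detect a difference of 5 mm assuming a standard deviation of 10 mm in the VAS", giving "64 patients per treatment arm" and 221 in total after allowing for 15% dropout. Section 16.0 plans about 222 patients, 74 per arm.

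**The concern.** A t-test or Wilcoxon test compares two groups, and the trial has three, so the VAS analysis must be a set of pairwise tests. The objectives and background suggest which pairs matter, but Section 9.2 does not say which will be run, which comes first, or what result would count as success. A claim could then rest on whichever pair turns out significant, and 5% is not the error rate of a claim reached that way.

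The choice of pair also decides what the claim means. CSL and CSS have the same volume and differ in lidocaine. CSS and CS differ in added volume. CSL and CS differ in both. If effects are additive, CSL v CS shows the largest difference and is the most likely to be significant, yet it cannot separate lidocaine from volume, which is what the saline arm is there to do.

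The schedule does not supply the missing time point either, because the six days in Section 9.2 match none of the times at which VAS is collected.

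**Working it through.** **Inputs.** Three equal arms; two-sided 0.05 (Section 9.2); difference 5 mm, SD 10 mm, 64 per arm, 15% dropout (Section 9.1); 74 enrolled per arm (Section 16.0). Power is not stated. I assume 80%, because it reproduces the plan's figure.

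**1. The plan's own sample size.** n per arm = 2 × (1.960 + 0.842)² × (10/5)² = 62.8, so 63. The t-based solution is 63.8, so 64. Then 3 × 64 × 1.15 = 220.8, so 221. The figures fit one two-arm comparison at 0.05.

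**2. Familywise error at one time point, all arms equal, no adjustment.**
- One contrast named in advance: 5%.
- Two contrasts sharing an arm: each difference has variance 2σ²/n and their covariance is ±σ²/n, so the correlation is ±0.5. From the bivariate normal, 1 − P(|Z1| < 1.96 and |Z2| < 1.96) = 9.07%. This applies to CSL v CS with CSL v CSS, and to CSL v CSS with CSS v CS.
- All three pairs: from the studentized range for three groups, P(Q > √2 × t(0.975; 189)) = 12.18%.
- Simulated t-tests (400,000 replicates, 64 per arm): 9.09% and 9.02% for the two sets of two contrasts, 12.22% for three pairs.
- Simulated Wilcoxon tests (40,000 replicates): 9.15% for CSL v CSS with CSS v CS, 12.27% for three pairs.

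Treating the tests as independent would give 1 − 0.95² = 9.75% and 1 − 0.95³ = 14.3%. Both are too high because the pairs share arms.

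**3. Overall F test at 0.05, then pairs at 0.05 only if it is significant.** With exactly three arms, either all means are equal, and the F test limits error to 5%, or at most one pair is equal, and that pair's own test limits it to 5%. Simulated familywise error at 64 per arm is 5.0% with all arms equal. With one equal pair it is 4.9% for CSL/CSS/CS means of 5/0/0, 5/5/0 and 0/5/0, and 5.0% for 20/0/0 and 20/20/0.

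**4. Power, before and after the gate (SD 10 mm).**

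| Per arm | Contrast | Means CSL/CSS/CS (mm) | Ungated | Gated |
|---|---|---|---|---|
| 64 | CSL v CSS | 5/0/0 | 80.2% | 76.0% |
| 64 | CSS v CS | 5/5/0 | 80.2% | 76.1% |
| 64 | CSL v CS | 5/2.5/0 | 80.0% | 69.7% |
| 64 | CSL v CSS | 5/2.5/0 | 28.9% | 27.8% |
| 64 | CSS v CS | 5/2.5/0 | 28.9% | 27.7% |
| 74 | CSL v CSS | 5/0/0 | 85.6% | 82.5% |
| 74 | CSL v CS | 5/2.5/0 | not run | 76.8% |

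With means 5/2.5/0, the pair that mixes drug and volume has 80% ungated power, and each pair that separates them has 29%.

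**The case against.** The strongest reply is that the protocol does say what it wants to compare. Section 1.1 sets CSL against CS and against CSS, and Section 2.2 repeats this and adds volume as a further question. That is correct, and a reader who inferred that the pairs appear nowhere would be wrong. What stands is that Section 9.2 neither carries those pairs into the analysis nor ranks them.

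A second reply is that 9% to 12% depends on the decision rule. This also stands. Each single test keeps its 5% level, and one contrast named primary would have 5%. If lidocaine had to differ from both comparators in the same direction, simulation gives 0.9% when all arms are equal, and each test's own level caps the error at 5% when only one contrast is null. Whether distinct questions need joint error control is partly judgement. The difficulty is that the plan states no rule.

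A third reply is that CSL v CS is a stated objective and should not be discarded. I agree. Its limit is one of interpretation, and the loss of power on it is a real cost.

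A fourth is that the gate is not the only remedy. Testing in a fixed order, CSL v CSS first, keeps 80% power for that contrast but costs power for later ones. Bonferroni at 64 per arm gives 71% for two contrasts and 66% for three.

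A reader might also infer a much larger inflation from repeated testing over days. The documents do not support a figure: Section 9.2 does not state tests at the collected times, its six days have no scheduled VAS, and the correlation between times would have to be assumed.

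**Conclusion.** The concern holds in a limited form. Section 9.2 leaves a three-arm primary outcome to unadjusted two-group tests, without an overall test, named or ranked contrasts, or a usable primary time point. If any significant pair can support a claim, familywise error at one time point is about 9% for two contrasts sharing an arm and about 12% for all three. These figures assume equal arms, no true differences and, for the simulations, normal data. They are not the trial's established error rate, since the plan fixes no decision rule.

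The point is confined to VAS. Section 9.2 says "Chi-square tests will be used to compare treatment groups for categorical variables", and each of those can be a single three-group test, so it would be wrong to extend the finding to them. The choice between t-test and Wilcoxon, the status of efficacy as an endpoint, and the interim look are separate matters and do not enter these figures.

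This should be fixed but does not undermine the design: each test is valid alone, and the trial already has the arms needed to answer both questions.

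**What to change.** Amend Section 9.2 before unblinding. The section provides the route: "Any deviations from the previously described statistical plan will be described and justified in a protocol amendment".

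- Name one primary VAS time point from 1 minute, 10 minutes and 6 weeks, in place of the six days. The 1-minute score fits the immediate-pain question in Section 2.2. Report the other times as secondary.
- At that time point, run a three-arm overall F test at two-sided 0.05. Test the three pairs at 0.05 only if it is significant.
- Keep CSL v CS as a stated objective. Rest the claim about lidocaine itself on CSL v CSS, and the claim about volume on CSS v CS.

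The cost is an amendment and some power. At 64 analysed per arm, a 5 mm contrast goes from 80% to 76% when the third arm equals one of the pair, and CSL v CS goes from 80% to 70% when CSS lies midway. State these figures in the plan rather than enrol more patients. If all 74 per arm give a same-visit score (an assumption), gated power is about 83% and 77% respectively. For 6-week VAS, 74 × 0.85 = 62.9 per arm would remain, so the figures for 64 are the relevant guide. No treatment or clinical procedure changes.

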1.0 Objectives

1.1 Study Objectives

- Compare pain, using a visual analog scale (VAS), associated with corticosteroid/lidocaine injection (CSL) to corticosteroid injection alone (CS) and corticosteroid/saline (CSS) injection.
- Review any adverse events related to the three treatment groups (CSL, CS and CSS).
- Review the efficacy of the three treatment groups (CSL, CS and CSS).
- Subcategorize patients based on demographic variables, comorbid conditions and anatomic location.

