1.3 Secondary Study Endpoints

- Incidence of adverse effects
- Presence of clicking/locking (yes/no)
- Patient satisfaction (yes/no)
- Time to stopping medication
- Need for additional analgesics
- Effectiveness of injection

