7.2 Study Procedures**7.2.1 Visit 1 – Screening/Baseline Visit**

Patients will be given information about the study and asked to participate. If eligible, based on inclusion and exclusion criteria, informed consent will be obtained at the time of the screening visit and the patient will be enrolled in the study.

After obtaining informed consent, the patient will be randomized to one of three treatment groups. The study investigator (who is unblinded) will randomly draw a sealed envelope

containing one of the three treatment groups. The sealed envelopes will be stored in a secure area within the clinic practice site.

- CS – corticosteroid alone -1 cc dexamethasone (4mg/ml) only
- CSL – corticosteroid/lidocaine combination - 1 cc dexamethasone (4mg/ml) and 1 cc 1% lidocaine
- CSS – corticosteroid/saline combination - 1 cc dexamethasone (4mg/ml) and 1 cc 0.9% injectable saline)

The patient will then be asked to complete a Patient Survey pre-injection (VAS Pain Scale and Trigger question). The study investigator will perform a single injection using a 25 gauge 1.5" needle. The needle will be inserted at 90 degrees to the skin, 1 cm proximal to the metacarpophalangeal joint flexion crease. The injections will be prepared in the Bone & Joint Institute as part of standard of care.

The patient will then complete the Patient Survey at 1 minute and 10 minutes following injection (VAS Pain Scale and Trigger question).

Objective hand exam will be performed including range of motion at MP, PIP and DIP joints, presence of clicking or locking, triggering score, pain with range of motion and grip strength as part of the patient's standard of care.

7.2.2 6-Week Follow-Up Phone Call

The patient will be contacted via phone and will be asked to verbally complete the Patient Survey (patient will be asked to report the VAS Pain score over the phone in .5 increments – i.e. 3.5, 4.0, 5.0, 5.5, etc.) and the coordinator will record the score. The patient will also answer question about how often he/she triggers (see phone script).

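### Section 9.2 compares adverse events by assigned arm under intention to treat and defines no safety population; analysing them by injection received is a small, free improvement

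*Combined protocol and SAP*

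**What the plan says.** Section 1.1 makes harms an objective: "Review any adverse events related to the three treatment groups (CSL, CS and CSS"). Section 1.3 makes them a secondary endpoint: "Incidence of adverse effects". Section 12.0 names a risk specific to one arm: "Allergic reaction to lidocaine or the preservative used in lidocaine".

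Section 9.2 sets the test: "Chi-square tests will be used to compare treatment groups for categorical variables (satisfaction, presence of clicking/locking, adverse events"). It then sets the analysis basis for every comparison between arms: "All analyses comparing the treatment groups will be conducted on an intention-to-treat basis". Sections 11 and 21 deal with collecting, judging and reporting adverse events. They do not say which patients form the denominator or to which arm an event is counted.

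Section 7.2.1 gives the order of steps at the single clinic visit. First, "After obtaining informed consent, the patient will be randomized to one of three treatment groups". Next, "The patient will then be asked to complete a Patient Survey pre-injection (VAS Pain Scale and Trigger question"). The injection follows. Section 3.3.2 keeps data collected up to withdrawal. It gives no rule for a patient who was randomised but not injected, or who was given another arm's injection.

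**The concern.** Intention to treat protects the comparison of pain and efficacy. For harms the question is what happened to patients who received a given injection, and the protocol's own definitions in section 21.1 tie an adverse event to use of the drug. Section 9.2 nevertheless compares harms by assignment.

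Two kinds of patient make the difference. A patient assigned CSS but injected with CSL in error, who then reacts to lidocaine, would be tabulated in an arm that contains no lidocaine. A patient who leaves between randomisation and injection cannot have an injection-related event, but under a literal intention-to-treat reading would still count in the denominator. CSL and CSS have the same volume (1 cc plus 1 cc), so volume alone would not reveal a swap between them.

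If such errors are unrelated to a patient's risk and similar across arms, they push the observed rates together, towards a finding of no difference in harm. That matters to a trial that asks whether lidocaine is an unnecessary addition.

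**Working it through.** **The plan's own figure.** Section 9.1 gives a 5 mm difference, an SD of 10 mm, 15% dropout, 64 per arm and 221 in total. Power is not stated; 80% is assumed here. A two-sided 5% t-test then needs 64 per arm (power 0.801). Three arms give 3 × 64 = 192, and 192 × 1.15 = 220.8, which rounds to 221. The figure reproduces and does not depend on how adverse events are analysed. Section 16.0 plans 74 per arm, which is used below.

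**Effect of counting by assigned arm.** Let p_own and p_other be the adverse-event rates by injection received, u the share of each arm never injected (no injection-related event, but kept in the denominator), and x the share of each arm given the other arm's injection. Then:

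- assigned-arm rate = (1 − u − x) × p_own + x × p_other
- assigned-arm difference = (1 − u − 2x) × as-received difference

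The documents give none of these rates, so every value below is an assumption.

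Swaps only, between CSL and CSS (u = 0):

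- x = 1%: 1 − 0.02 = 0.98, a shrinkage of 2%
- x = 2%: 1 − 0.04 = 0.96, a shrinkage of 4%
- x = 5%: 1 − 0.10 = 0.90, a shrinkage of 10%

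With non-injection added, at 74 per arm. Power is for two proportions by the normal approximation, two-sided 5%: Φ{[d√n − 1.96√(2p̄(1 − p̄))] / √(p₁(1 − p₁) + p₂(1 − p₂))}, where d = p₁ − p₂ and p̄ is the mean of the two rates.

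| Assumed as-received rates | u | x | Factor | Difference (points) | Power |
|---|---|---|---|---|---|
| 20% v 5% | 0 | 0 | 1.00 | 15.0 | 0.794 |
| 20% v 5% | 2% | 0 | 0.98 | 14.7 | 0.784 |
| 20% v 5% | 0 | 2% | 0.96 | 14.4 | 0.760 |
| 20% v 5% | 5% | 2% | 0.91 | 13.65 | 0.733 |
| 20% v 5% | 10% | 5% | 0.80 | 12.0 | 0.639 |
| 10% v 2% | 0 | 0 | 1.00 | 8.0 | 0.536 |
| 10% v 2% | 5% | 2% | 0.91 | 7.28 | 0.480 |
| 10% v 2% | 10% | 5% | 0.80 | 6.4 | 0.405 |

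The rows with 10% uninjected and 5% swapped are an outer bound, not an expectation: 5% of 74 is 3.7 wrong injections in each arm. With u = x = 0 the two analyses are the same.

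**A single event.** One event is 1/74 = 1.35 percentage points of an arm. Suppose there are two lidocaine reactions and one falls in a CSS-assigned patient, so that 2 v 0 is tabulated as 1 v 1. The uncorrected chi-square for 2/74 v 0/74 is 148 × (2 × 74)² / (2 × 146 × 74 × 74) = 2.03, p about 0.15; Fisher's p is about 0.50. The 2 v 0 result is already well short of the 0.05 level in 9.2. The chance of exactly that split is 2x(1 − x): about 2% at x = 1% and 9.5% at x = 5%.

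**The case against.** The strongest reply is that the problem has almost no room to arise. Treatment is one injection at the randomisation visit. The unblinded investigator draws the envelope, and the unblinded physician who prepares the injection also gives it. There is no repeat dosing or switching, and only a short survey stands between assignment and injection. Section 7.4.6.1 also says that existing dispensing policies will be followed. Sections 11.5 and 11.6 have adverse events reviewed as they occur, and section 21.3 has an investigator judge causality, so a lidocaine reaction after a wrong injection could be recognised case by case. All of this stands, and it is why the point is small. It does not change the arm in which the chi-square would count the event.

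A reader might infer two stronger claims, and the documents support neither.

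- **That the plan counts uninjected patients as exposed.** No section states the adverse-event denominator. Section 3.3.2 ends data collection at withdrawal and includes only what was collected before. Keeping such a patient in the denominator is an inference from the intention-to-treat sentence.
- **That one misplaced event could erase a safety finding.** The 2 v 0 example above is non-significant before any misplacement, so no formal conclusion is lost.

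Nor can it be said that the injected contents go unrecorded: the Visit 1 form is not among the documents.

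**Conclusion.** The point holds as a free improvement, and a small one. Section 9.2 states a rule for harms that is less suitable than the conventional alternative of analysing them by injection received, and no other section modifies it. On assumed symmetric swap rates of 1% to 5% between CSL and CSS, the difference in adverse-event rates shrinks by 2% to 10%. The likely effect is at or below the lower end, and it is nil if every randomised patient receives the assigned injection. The calculation assumes that swaps and non-injection are unrelated to event risk and equally common in the arms compared. The documents give no event, swap or non-injection rates with which to narrow the range. The pain comparison and the sample size are untouched.

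**What to change.** In 9.2, limit the intention-to-treat sentence to the pain and efficacy comparisons. Add that adverse events are analysed in all patients who received an injection, grouped by the injection actually received, and that any randomised patients who were not injected or were given another arm's injection are listed with assigned and received treatment. If the Visit 1 form does not already record the contents injected, add that field.

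The cost is one sentence and at most one form field, with no loss to the pain and efficacy analyses. It is best done before data are seen: 9.2 requires changes to the statistical plan to be justified in an amendment, and a switch made after a misassigned event is known would look data-driven.
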